5 STUDY POPULATION

5.1 INCLUSION CRITERIA

To be eligible to participate in this study, an individual must meet all the following criteria:

- 1) Age 18-65 years.
- 2) An Alcohol Use Disorders Identification Test (AUDIT) score of 8 or higher.
- 3) Ability to read and speak English.
- 4) Ability to provide written informed consent.
- 5) Breath alcohol of 0.00 during informed consent.
- 6) Operate a smartphone with an active service provider.

5.2 EXCLUSION CRITERIA

An individual who meets any of the following criteria will be excluded from participation in this study:

- 1) Diagnostic and Statistical Manual of Mental Disorders, Fifth Edition (DSM-5) alcohol use disorder, severe type.
- 2) Significant risk of dangerous alcohol withdrawal, defined as a history of alcohol detoxification or seizure in the last 12 months and expression of concern by the participant about dangerous withdrawal.
- 3) Diagnosis of a psychotic disorder.
- 4) Lifetime suicide attempt or suicidality in the past year.
- 5) Any other medical or psychiatric condition that would compromise safe participation.

5.3

5.4 SCREEN FAILURES

Screen failures are defined as participants who consent to participate in the study but are not subsequently assigned to the study intervention or entered in the study. Individuals who do not meet the criteria for participation in this trial (screen failure) because of meeting one or more exclusion criteria that are likely to change over time may be rescreened. Examples include the successful treatment of a previous affective DSM-5 alcohol use disorder, severe type, and overcoming the significant risk of dangerous alcohol withdrawal, defined as a history of alcohol detoxification or seizure in the last 12 months and expression of concern by the participant about dangerous withdrawal. Rescreened participants will be assigned the same participant number as for the initial screening.

5.5 STRATEGIES FOR RECRUITMENT AND RETENTION

We anticipate a 5-month recruitment period, necessitating n=4 recruited per month which is far below our normal recruitment rates. Flyers will advertise the study, and staff and providers will be aware of the study and will be asked to refer potentially interested participants to our investigation. As noted elsewhere, while

we will partner with clinics we will also recruit from the community. After an initial phone screening, those deemed eligible will be scheduled for an in-person study interview, during which they will provide informed consent and complete baseline data collection. During this time, participants will also receive a brief tutorial on how to use the BACtrack breathalyzer and how it integrates with the application on their smartphone. Participants who do not have a compatible iPhone Operating System (iOS) smartphone will be provided one for this study. The phones will be supplied from a testing inventory maintained by Managed Health Connections.

Participant set-up instructions will also describe the time window for reporting the definition of zones of use and will be provided contact information for technical support to be used during the study. During the baseline visit participants will receive a \$30 gift cards for their time.

During the first A phase, participants will receive \$2 per sample (regardless of being positive or negative for breath alcohol) submitted instantly, for a maximum payout of \$6 per day.

During the B phase, participants will begin by receiving \$2 per alcohol negative breath sample submitted, escalating by \$0.25 per alcohol negative breath sample submission until a maximum value of \$3.50 per sample is reached. Once this value is reached based on negative breath sample submissions, participants will continue to receive \$3.50 per alcohol-negative breath sample submission. If a participant submits an alcohol positive breath sample, they will be reset to \$2.00 per sample and will need to work up to receive \$3.50 per sample again. Final onetime payment of \$50 will be provided to participants upon return of study devices. Participants will receive electronic payment through a gift card. Payments will be loaded onto the card weekly.

6 STUDY INTERVENTION(S) OR EXPERIMENTAL MANIPULATION(S)

We will use the first A phase of data collection to define personalized 'cold' (i.e., lower than 50% probability of drinking) and 'hot' (i.e. greater than 50% probability of drinking) spots using the participant's geospatial location data (via smartphone). As part of this CM system, participants will have the capability to receive multi-modal message reminders when they enter a new window of needed biochemical sample submission and additional reminders when the window of sample submission is about to close. While participants will receive information messages to this effect during the A phase, participants will receive additional personalized multi-modal message reminders once our CM platform can detect that they have entered a cold or hot zone. This will be based on the participant entering a 2/10s (i.e., approximately 1,000 feet) of a mile radius near a cold or hot zone. For example, upon entering a hot zone radius during the B phase wherein they had 50% or greater likelihood of drinking in that zone during the A phase, they will receive a text message encouraging them to change surroundings in order better promote abstinence. Also, if the participant is within a window of time where they are eligible to submit a sample and receive a dose of reinforcement, this is another action that the individual can take to help bolster their attempt to remain abstinent. All of these data (e.g., biochemical results, location of sample submission, time of submission) will be warehoused in the individual's EMR to be presented in summary form on their primary care provider's dashboard. This will help the provider give counsel or otherwise devise an action plan if the patient's drinking behavior is proving impervious to intervention or if the patient's goals are being met, this is something the provider can encourage.

7 STUDY INTERVENTION/EXPERIMENTAL MANIPULATION DISCONTINUATION AND PARTICIPANT DISCONTINUATION/WITHDRAWAL

7.1 PARTICIPANT DISCONTINUATION/WITHDRAWAL FROM THE STUDY

Participants are free to withdraw from participation in the study at any time upon their request.

An investigator may discontinue a participant from the study for the following reasons:

- Significant study intervention non-compliance unless varying compliance is an aspect of the study objectives.
- Lost-to-follow up; unable to contact subject.
- Any event, medical condition or situation occurs such that continued collection of follow-up study data would not be in the best interest of the participant or might require an additional treatment that would confound the interpretation of the study.
- The participant meets an exclusion criterion (either newly developed or not previously recognized) that precludes further study participation.

The reason for participant discontinuation or withdrawal from the study will be recorded on REDCap.

In this situation, participants will be asked to bring back the phone, fill out the exit questionnaire and received a \$50 gift card.

7.2 LOST TO FOLLOW-UP

A participant will be considered lost to follow-up if they fail to return for a scheduled visit and study staff are unable to contact the participant after at least 3 attempts.

The following actions must be taken if a participant fails to return to the clinic for a required study visit:

- The site will attempt to contact the participant, reschedule the missed visit, counsel the participant on the importance of maintaining the assigned visit schedule and ascertain if the participant wishes to and/or should continue in the study.
- Before a participant is deemed lost to follow-up, the investigator or designee will make every effort to regain contact with the participant (where possible, 3 telephone calls and, if necessary, a certified letter to the participant's last known mailing address or local equivalent methods). These contact attempts will be documented in the participant's study file.
- Should the participant continue to be unreachable, he or she will be considered to have withdrawn from the study with a primary reason for loss to follow-up.
- Study phone provided at baseline will be disable remotely.

8 STUDY ASSESSMENTS AND PROCEDURES

8.1 ENDPOINT AND OTHER NON-SAFETY ASSESSMENTS

Our primary outcome is biochemically confirmed alcohol abstinence, measured thrice daily throughout the 8-week study. Age and risky drinking will be determined based on self-report at the screening interview. Risky NIH Clinical Trial Protocol

drinking will be defined using the AUDIT and AUD diagnosis will be confirmed by administering the DSM-5 checklist. Research staff will also use this interview to assess for possible exclusionary cognitive or psychotic disorders using the MINI Neuropsychiatric Interview (M.I.N.I.). At baseline data collection, potential participants will complete a medical history form.

Secondary outcomes will include self-reported alcohol use measured by the Timeline Follow Back to assess the frequency and amount of daily drinking via multi-modal EMA data collection. The Addiction Severity Index and the quality of life in several domains (e.g., psychiatric, legal, medical) will be assessed at baseline. The EMA application will also collect data to assess craving and withdrawal for alcohol and tobacco by using a 1 to 5 Likert scale along with location and activity at the time of the report. Other substance use, including amphetamine, methamphetamine, cocaine, and marijuana, will be measured by urinalysis at baseline. We will characterize the psychiatric health of the participant sample by measuring psychopathology with the Brief Symptom Inventory, which assesses anxiety, depression, impulsiveness, and suicidality. We will also use the Fagerström Test of Nicotine Dependence to measure the severity of tobacco dependence and the Alcohol Use Disorders Identification Test to measure the severity of alcohol use disorder.

Our study variables and the schedule of data collection are summarized in **Table 2**.

Table 2. Data collection schedule

| Measure | Baseline Week 0 | A-B-A Week 1-8 |
|--------------------------------------------------------------------|----------------------------------|---------------------------------|
| Eligibility Criteria | | |
| Demographics | ✓ | |
| MINI Research Psychiatric Diagnosis | ✓ | |
| Medical history form | ✓ | |
| Other inclusion/exclusion criteria | ✓ | |
| Primary Outcomes | | |
| Alcohol use (biochemical BAC) | ✓ | 3 times per day |
| Secondary Outcomes | | |
| Alcohol Timeline Follow Back (self-report) | ✓ | |
| Addiction severity: ASI-Lite (self-report) | ✓ | |
| Alcohol cravings and withdrawal: visual analog scale (self-report) | ✓ | 3 times per day |
| Location and Activity at time of the report | ✓ | 3 times per day |
| Other substance use (biochemical) | ✓ | |
| Health-related quality of life (self-report) | ✓ | |
| Tobacco dependence (Fagerström) | ✓ | |
| Alcohol dependence (AUDIT) | ✓ | |
| Psychopathology (BSI) | ✓ | |
| Follow up phone call | ✓ | Weekly |
| Sleepiness Scale | ✓ | Weekly |

8.2 SAFETY ASSESSMENTS

Qualified personnel will perform the study according to the WSU IRB-approved application. The equipment, facilities, and procedures to be used in this research meet recognized standards for safety. We will assess participants alcohol use three times daily through the Automated Reinforcement Management System (ARMS) which will provide the following functions: Breathalyzer recording, EMA responses, and eventually geospatial mapping Patient Dashboard, and a Clinician Dashboard. The participant will be provided with a BACtrack breathalyzer device. The setup process will pair their phone with the breathalyzer device and establish a profile including locations and time of day for reporting. The mobile application will provide the participant user with the ability to input EMA information and control the breathalyzer function. It will utilize a hybrid iOS/mobile web application architecture for phase 1 enabling the integration of breathalyzer and geographic information with web-based dashboard information. The participant will be prompted to record EMA and breathalyzer samples based on their profile information and prior reporting. During a reporting window, the participant will receive a prompt to initiate breathalyzer measurement within the thirty (30) minute time window. The application will automatically record the location of the breathalyzer sample and categorize it as a "hot" or "non-hot" zone for future analysis. Following the breathalyzer report, the participant will be prompted to respond to EMA questions. Following the data entry, the participant will receive a multimedia message describing their progress and sample tailored messaging offering resources for additional information. To support compliance, if a participant does not record substance use in real-time and does not respond to the daily check-in, the system will send reminders. The reminders are multi-modal as they can reach the user through different means based on user preference. For the study, we will rely on application delivered PUSH messages for the assigned smartphones with text message back up and the option for voice calls from Research Coordinator. If the participant does not respond to the application and does not respond to reminders, their name and status will be communicated to the research coordinator. The research coordinator could place a personal call to the participant to follow up. The application provides a dashboard for each patient to show how the EMA answers are related to substance use outcomes. It informs the patient of progress toward CM rewards and provides suggestions regarding which factors are most likely to be associated with craving and substance use. Responses to EMA-assessed factors will provide the basis for creating a menu of customizable strategies to improve goal adherence for individuals and/or modify incentives. Certain patterns of responses will trigger the app to employ specific strategies to help the participant achieve his goal.

8.3 ADVERSE EVENTS AND SERIOUS ADVERSE EVENTS

8.3.1 DEFINITION OF ADVERSE EVENTS

According to the code of federal regulation title 21 of the Food and Drug Administration FDA, An Adverse event refers to any untoward medical occurrence associated with the use of a drug in humans, whether considered drug-related or not.

All AEs, whether volunteered, elicited, or noted on physical examination, will be recorded throughout the study (i.e., from signing of the ICF until completion).

All AEs will be collected in a proper case report form and recorded in REDCap.

8.3.2 DEFINITION OF SERIOUS ADVERSE EVENTS

An adverse event or suspected adverse reaction is considered "serious" if, in the view of either the investigator or sponsor, it results in any of the following outcomes: Death, a life-threatening adverse event, inpatient hospitalization, prolongation of existing hospitalization, a persistent or significant incapacity/substantial disruption of the ability to conduct normal life functions, or a congenital anomaly/birth defect.

Important medical events that may not result in death, though life-threatening or require hospitalization may be considered serious when, based upon appropriate medical judgment, they jeopardize the life or require medical or surgical intervention to prevent one of the outcomes listed in this definition. Examples of such medical events include allergic bronchospasm requiring intensive treatment in an emergency room or at home, blood dyscrasias or convulsions that do not result in inpatient hospitalization, or the development of drug dependency or drug abuse. SAEs are life-threatening adverse events or life-threatening suspected adverse reactions. An adverse event or suspected adverse reaction is considered "life-threatening" if, in the view of either the investigator or sponsor, its occurrence places the patient at immediate risk of death. It does not include an adverse event or suspected adverse reaction that, had it occurred in a more severe form, might have caused death.

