8.3.6 SERIOUS ADVERSE EVENT REPORTING

The SAE form must be completed as thoroughly as possible with all available details of the event, signed by the investigator (or appropriately qualified designee), and emailed or faxed to medical monitor within 24 hours of first becoming aware of the event. Such SAE will be reported to the Ringful and, the WSU IRB within 24 hours of first becoming aware of the event.

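### Section 8.3.2 defines a serious adverse event in two incompatible ways, and 8.3.1 ties adverse events to drug use in a trial without a study drug, so classification and reporting deadlines are ambiguous

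*Protocol*

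**What the plan says.** Section 8.3.2 opens with a list. An event is serious if, in the investigator's or sponsor's view, "it results in any of the following outcomes: Death, a life-threatening adverse event, inpatient hospitalization, prolongation of existing hospitalization", or if it causes lasting or significant incapacity or a congenital anomaly. A second paragraph lets important medical events count as serious on medical judgment. One of its examples is "blood dyscrasias or convulsions that do not result in inpatient hospitalization". The same paragraph then says "SAEs are life-threatening adverse events or life-threatening suspected adverse reactions". It goes on to define life-threatening as immediate risk of death and adds the limit "It does not include an adverse event or suspected adverse reaction that, had it occurred in a more severe form, might have caused death".

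Section 8.3.1 defines an adverse event as "any untoward medical occurrence associated with the use of a drug in humans, whether considered drug-related or not", and then requires that "All AEs, whether volunteered, elicited, or noted on physical examination, will be recorded throughout the study".

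Three sections attach consequences to the classification:
- **8.3.6:** an SAE goes to the medical monitor, the company named there and the IRB "within 24 hours of first becoming aware of the event".
- **8.3.5:** the general IRB limit is seven working days.
- **8.3.4:** collection after the last day of participation runs 30 days for SAEs and seven days for non-serious events.

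**The concern.** The sentence after the list is written as a definition, not as an illustration, and nothing in the protocol says which of the two texts prevails. A coordinator facing an admission that does not put the participant at immediate risk of death gets opposite answers from the same section.

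Such events are foreseeable. Participants have an AUDIT score of 8 or higher and are paid in the B phase for alcohol-negative samples. Section 8.3.3.3 assigns the expectedness judgment to a provider with expertise in alcohol withdrawal. Severe alcohol use disorder is excluded. However, the separate withdrawal-risk exclusion in 5.2 requires both a recent history of detoxification or seizure and concern expressed by the participant. The protocol gives no expected event rate, so the frequency cannot be estimated from it.

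The adverse event definition is a second mismatch. It presupposes drug use, while sections 4.1, 5.5 and 6 describe reinforcers, breath samples and messages, and 2.3.1 calls the intervention digital. Because 8.3.2 builds on the term adverse event, the poor fit carries over into the SAE definition.

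**Working it through.** The plan has no figure to reproduce here. The check sets the texts side by side.

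**Step 1. Outcomes in 8.3.2 under each text.** The list names six outcomes. The restrictive sentence keeps life-threatening events explicitly. It also keeps death in substance, because a fatal event meets the criterion of immediate risk of death.

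| Category in 8.3.2 | Serious by the list and the paragraph after it | Serious by the restrictive sentence |
|---|---|---|
| Death | yes | yes |
| Life-threatening event | yes | yes |
| Inpatient admission without immediate risk of death | yes | no |
| Prolonged admission without immediate risk of death | yes | no |
| Incapacity without immediate risk of death | yes | no |
| Congenital anomaly without immediate risk of death | yes | no |
| Important medical event without immediate risk of death, such as a convulsion without admission | may be | no |

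Outcomes in conflict: 6 − 2 = 4, plus the important-medical-event category, which stands outside the six.

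**Step 2. What the classification changes.**

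| Rule | If serious | If not serious |
|---|---|---|
| Reporting limit | 24 hours (8.3.6) | at most seven working days to the IRB, if reportable (8.3.5) |
| Collection after last day of participation | 30 days (8.3.4) | 7 days (8.3.4) |

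**Step 3. A worked case.** Take an admission without immediate risk of death that starts 20 days after the last day of participation. By the list it is an SAE: 20 ≤ 30, so it is collected and reported within 24 hours. By the restrictive sentence it is non-serious: 20 > 7, so it falls outside the collection window.

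**Step 4. Effect on the safety tables.** Section 9.3.4 presents serious treatment-emergent events in a table or listing. With 20 planned participants, one participant whose only serious event is reclassified moves the proportion with an SAE by 1/20 = 5 percentage points.

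**Step 5. The adverse event term.** Section 8.3.1 refers to drug use. Section 8.3.3.2 assesses relationship to the study intervention, 8.3.3.3 assesses expectedness against the risks described for the study procedures, and 9.3.4 tabulates relationship to the study intervention. The later sections therefore need a broader concept than 8.3.1 defines. Two of the action-taken options in 8.3.3.2 mention medication although no study medication is described. One of these is mixed and also covers a stopped study procedure.

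**The case against.** The best reply is that the section is clear enough if read as a whole. Its stated criterion is any one of the listed outcomes, and it names convulsions without admission as a possible serious event. The disputed sentence stands directly before the definition of life-threatening and reads like a garbled lead-in to it. On that reading the broad list governs and nothing is lost.

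Other parts of the protocol also show that events are meant to be captured. Table 1 schedules adverse events weekly. Section 8.3.4 has the coordinator record events from consent onward and the investigator ask at each visit. Sections 8.3.3.2 and 8.3.3.3 refer to the intervention and procedures, not to a drug. Section 10.1.8 offers an IRB form for any event, including one that staff cannot classify.

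Most of this stands. It rules out three stronger inferences that a reader might draw:
- **That the definitions miss the events this trial could produce.** The broad list is still in force and the capture provisions are explicit.
- **That the restrictive sentence drops five of the six outcomes.** Death meets the life-threatening criterion, so four are in conflict.
- **That no event can qualify under 8.3.1.** The wording refers to use of a drug, not of a study drug, and disclaims any need for drug causality. Section 9.3.4 codes participants' medications, so some drug use in the sample is foreseen.

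The reply does not remove the contradiction. The sentence is unqualified, it follows the list, and no precedence is given. Seeing it as a slip requires the reader to correct the text, and staff working to a 24-hour deadline should not have to do that.

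**Conclusion.** The point holds as an internal contradiction in 8.3.2 together with an ill-fitting adverse event definition in 8.3.1. On the literal text, four of the six listed outcomes and the important-medical-event category have two answers when there is no immediate risk of death. The difference is 24 hours against at most seven working days for reporting, and 30 days against seven for collection. The expected harm is inconsistent classification and reporting, not wholesale loss of events.

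This rests on three readings: that the restrictive sentence can be taken as a definition, as it is worded; that a fatal event counts as life-threatening; and that the scattered mentions of medication do not describe a study drug, since no section on the intervention describes one.

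The primary endpoint, the analysis model and the sample size are unaffected. The correction should be made because two operative safety rules are wrong as written and the remedy is cheap.

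**What to change.** Three wording edits:
1. **8.3.2:** reconcile the two texts. Either delete the restrictive sentence or reword it so that it only introduces the definition of life-threatening and no longer states what an SAE is.
2. **8.3.1:** define an adverse event as any untoward medical occurrence in a participant during the study, whether or not considered related to the study intervention. This matches 8.3.3.2 and 9.3.4.
3. **8.3.3.2, action taken:** remove only the references to study medication. Keep an option for a stopped study procedure. Deleting the mixed option outright would remove the only named way to record that.

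The case report form and the SAE form should follow the same wording. No endpoint, sample size or analysis changes. The cost is a protocol amendment and possibly a few more events recorded or reported on the 24-hour timeline.
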